7. STATISTICAL METHODS AND DETERMINATION OF SAMPLE SIZE

7.1 STATISTICAL DESIGN - MODEL

This is a Phase I/II, open-label trial (including a Phase I dose finding and a Phase I MTD expansion cohorts/Phase II part) to explore the safety and possibly early signs of efficacy of afatinib in paediatric patients with neuroectodermal tumours, rhabdomyosarcoma and/or other solid tumours with known ErbB pathway deregulation regardless of tumour histology.

- The dose finding part will use a rolling 6 design and recruit up to 30 patients who are evaluable for DLT to determine the MTD.
- In the MTD expansion cohorts/Phase II part, a minimum of 5 patients in each of the following cohorts, i.e. HGG, DIPG, EM and a mixed histology agnostic cohort of patients with refractory tumours, will be accrued. All patients must fulfil two of the biomarker screening criteria, i.e. EGFR FISH positive and/or EGFR H-score >150 and/or HER2-DDISH positive and/or HER2 H-score > (see [Section 3.3.2](#)). An exploratory cohort will recruit patients with proven genomic, transcriptomic or proteomic alterations which are not defined above. All patients must be evaluable for OR/efficacy. Further safety data will be collected.

7.2 NULL AND ALTERNATIVE HYPOTHESES

No formal hypothesis testing is planned in this trial. All analyses will be descriptive and exploratory in nature.

7.3 PLANNED ANALYSES

All patients who receive at least one dose of afatinib will be included in the analysis for safety and efficacy and they are defined as treated set.

7.3.1 Primary analyses

Dose finding part:

In order to determine the MTD, the number of patients with DLT deemed to be related to administration of afatinib will be assessed based upon the patients in dose finding part of the trial. (See [Table 4.1.4.1:2](#)). The advanced disease of the patients in this trial makes it possible that significant adverse events, including events that would qualify as DLT, will occur, but will not be caused by afatinib. The MTD will be determined as the highest dose at which no more than 1/6 patients experienced DLT considered related to afatinib. (See [Table 4.1.4.1:1](#))

Proprietary confidential information.

© 2017 Boehringer Ingelheim International GmbH or one or more of its affiliated companies. All rights reserved.

This document may not - in full or in part - be passed on, reproduced, published or otherwise used without prior written permission.

Pharmacokinetics is a primary endpoint for the dose finding part. For details see [Section 7.3.5](#)

MTD expansion cohorts/Phase II part:

OR will be assessed when the last patient enrolled in the MTD expansion cohorts/Phase II part will be evaluable for efficacy.

Each patient will be assigned to one of the following categories based on investigator's assessment according to the institutional response evaluation criteria for the given tumour type, irrespective of protocol violation or missing data:

- CR (complete response)
- PR (partial response)
- SD (stable disease)
- PD (progressive disease)
- Not evaluable (not assessable, insufficient data)

Objective response is defined as CR and PR.

If the International Criteria for Neuroblastoma Response Criteria (INRC) ([R14-2418](#)) is used, each patient will be assigned to one of the following categories:

- CR (complete response)
- VGPR (very good partial response)
- PR (partial response)
- MxR (mixed response)
- NoR (no response)
- PD (progressive disease)

The objective response is then defined as CR, VGPR, PR or MxR.

OR will be tabulated and provided with the proportion and the exact 95% confidence interval based on all treated patients in the MTD expansion cohorts/Phase II part.

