7.3.2 Secondary analyses

In dose finding part, number of patients with OR will be described per dose level.

Proprietary confidential information.

© 2017 Boehringer Ingelheim International GmbH or one or more of its affiliated companies. All rights reserved.

This document may not - in full or in part - be passed on, reproduced, published or otherwise used without prior written permission.

In the MTD expansion cohorts/Phase II part, the PFS and DoR will be secondary endpoints. PFS is defined as the time from the date of first administration of treatment to the date of disease progression, or to the date of death, whichever comes first. The Kaplan-Meier estimates of PFS rate and 95% confidence intervals will be calculated at the time of each planned assessment. DoR is defined only for those patients with a response (CR or PR) as the interval between the date of randomization and the earliest date of disease progression. The Kaplan-Meier estimates of DoR and 95% confidence intervals will be calculated at the time of each planned assessment.

Pharmacokinetics is a secondary endpoint for the MTD expansion cohorts/Phase II part. For details see [Section 7.3.5](#).

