7.4 PRIMARY ENDPOINT(S)

7.4.1 Dose Finding Part:

One of the primary objectives is to assess the MTD based on the number of patients presenting DLTs during the MTD evaluation period. Therefore, an overall summary of DLTs (see CTP Section 4, Table 4.1.4.1.2 for the definition of DLTs) which occurred during the MTD evaluation period will be provided for each dose cohort from the dose finding cohort treated set. Patients who were replaced within the MTD evaluation period will be excluded from the determination of the MTD but will be considered for all other safety evaluations.

A summary of the number of patients with DLTs overall in any course will be also given by initial treatment and displayed in a similar format to the summary of DLTs occurring in the MTD evaluation period.

The determination of the MTD is based on a Rolling 6 design as illustrated in Section 4, Table 4.1.4.1:1 of the CTP. The MTD is defined as the highest dose at which no more than 1/6 patients experienced DLT considered related to afatinib during the MTD evaluation period. Refer to CTP 7.3.1 for further details on MTD evaluation.

Analysis of the standard PK endpoints is performed according to (2) and (8) as outlined in Section 7.3.5 of the CTP.

7.4.2 MTD expansion cohort part:

Objective response (OR) is defined as a best overall response of complete response (CR) or partial response (PR) based on investigator's assessment according to the institutional

response evaluation criteria for the given tumour type. If the International Criteria for Neuroblastoma Response Criteria (INRC) is used, OR is defined as complete response (CR), very good partial response (VGPR), partial response (PR) and mixed response (MxR). For further details on OR, please refer to CTP Section 7.3.1. The objective response rate will be calculated and reported as proportion of responders with 95% Clopper-Pearson CIs based on all treated patients. Objective response will be summarized regardless of confirmation.

Additional summary or listing may be provided for confirmed response. If only few patients (fewer than 5) achieved objective response, a detailed listing will be reported.

For objective responses, evaluated by institutional response evaluation criteria other than INRC, below confirmation rule for best overall response will be considered.

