- If CR or PR: look at all subsequent visits, if there is another CR or PR ≥ 28 days then the patient has a confirmed response. If there is not another CR or PR ≥ 28 days then the patient can be SD. Please note that once patient achieve CR any response other than CR will be considered as PD.

Detailed specifications are listed in Table 7.4.2: 1.

Table 7.4.2: 1 Confirmation rule for best overall response

Overall response (time point 1)	Overall response (subsequent time point)	Unconfirmed best overall response	Confirmed best overall response
CR	CR (≥ 28 days from 1)	CR	CR
CR	CR (< 28 days from 1)	CR	SD
CR	PR ¹	CR	SD
CR	SD	CR	SD
CR	PD	CR	SD
CR	NE/Missing	CR	SD
PR	CR (≥ 28 days from 1)	CR	PR
PR	CR (< 28 days from 1)	CR	SD
PR	PR (≥ 28 days from 1)	PR	PR
PR	PR (< 28 days from 1)	PR	SD
PR	SD	PR	SD
PR	PD	PR	SD
PR	NE/Missing	PR	SD

¹= If truly a CR at first response, any subsequent disease (even a PR relative to baseline) makes the disease PD. Could only be a PR if initial CR is changed to PR (i.e. not a true CR).

For INRC, a similar derivation of confirmed response will apply. That is, a subsequent assessment with the same or a better overall response on or after 28 days is required for the confirmation of an objective response, in the order from best to worst of CR > VGPR > PR > MxR. Otherwise, a SD will be considered as the confirmed best overall response.

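### Counting mixed response as objective response only under INRC gives the pooled primary ORR two responder thresholds and can only raise it, by 2.6 points per such patient at 38 patients

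*Protocol*

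**What the plan says.** The primary endpoint of the expansion part is objective response, assessed by the investigator under the institution's criteria for the tumour type. Protocol 7.3.1 then gives two responder rules.

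- General rule: "Objective response is defined as CR and PR".
- If INRC is used: "The objective response is then defined as CR, VGPR, PR or MxR".

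SAP 7.4.2 keeps both rules; its INRC list adds to CR "very good partial response (VGPR), partial response (PR) and mixed response (MxR"). When it sets out how an INRC response is confirmed, the same section orders the categories "in the order from best to worst of CR > VGPR > PR > MxR".

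Both rules enter one estimate. Protocol 7.3.1 asks for the "proportion and the exact 95% confidence interval based on all treated patients in the MTD expansion cohorts/Phase II part", and SAP 7.4.2 specifies the Clopper-Pearson interval. Confirmation is not needed for the reported rate: "Objective response will be summarized regardless of confirmation".

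Neither document defines MxR, explains why it counts, or plans an ORR without it.

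**The concern.** For all criteria but one, PR is the lowest category that makes a child a responder. Under INRC the bar sits one category lower, by the SAP's own ranking. A single proportion then mixes the two bars.

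This matters because of how the rate will be used. Protocol 7.2 plans no hypothesis test, and no numerical ORR target is set. Protocol 3.2 and 5.6.1 leave it to paediatric oncology experts and, in 3.2, to regulatory agencies to decide whether the rate is meaningful enough to continue development. With so few patients, that judgement rests on a handful of responders, so a reader needs to know that each one met a comparable standard, or to see where one did not.

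**Working it through.** **Inputs from the documents**

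- Up to 38 patients evaluable for response in the expansion part (Protocol 3.3).
- At least 5 in each of four cohorts (HGG, DIPG, ependymoma, mixed histology) and at most 6 in the exploratory cohort (Protocol 3.1).
- No neuroblastoma cohort. Such a patient can enter only through the mixed-histology or the exploratory cohort (Protocol 3.3.2).
- Not given: the expected number of INRC-assessed patients, and how often MxR would be the best response.

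**The plan's own response calculation.** Protocol Table 7.6:1 gives 67.2% as the chance of at least one response among 5 patients at a true rate of 20%. Check: 1 − 0.8^5 = 1 − 0.3277 = 67.23%. It reproduces. The formula gives every patient the same response probability and does not separate INRC patients from others.

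**Effect of the MxR rule.** Let r be the number of patients with best response CR, VGPR or PR, k the number of INRC patients with best response MxR, and N the denominator.

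- ORR as planned = (r + k)/N
- ORR without MxR = r/N
- Difference = k/N, which is zero or positive

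The exact 95% limits for x responders of N are the 2.5% quantile of Beta(x, N − x + 1) and the 97.5% quantile of Beta(x + 1, N − x). With N = 38 and, as an example, r = 2:

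| k | ORR without MxR (95% CI) | ORR as planned (95% CI) | Difference k/38 |
|---|---|---|---|
| 0 | 2/38 = 5.3% (0.6 to 17.7) | 2/38 = 5.3% (0.6 to 17.7) | 0 |
| 1 | 2/38 = 5.3% (0.6 to 17.7) | 3/38 = 7.9% (1.7 to 21.4) | 2.6 points |
| 2 | 2/38 = 5.3% (0.6 to 17.7) | 4/38 = 10.5% (2.9 to 24.8) | 5.3 points |

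The step depends on N. If accrual ended at four cohorts of 5 plus 6 exploratory patients, N = 4 × 5 + 6 = 26 and each MxR would add 1/26 = 3.8 points.

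**Does anything already planned remove the effect?**

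- The optional confirmed-response summary does not. Under SAP 7.4.2 an MxR followed at 28 days or later by the same or a better category is still a confirmed objective response.
- The detailed listing is required only with fewer than 5 responders, and MxR patients count towards that limit: 4 with CR or PR plus 1 with MxR makes 5, so the listing is no longer mandatory.
- Frequency tables by category (SAP 7) would show an MxR, but the headline rate and interval would still include it.

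**The case against.** The case for leaving the rule alone has real substance.

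- **It is a deliberate choice.** Protocol and SAP state the same INRC responder set, so this is not a drafting slip. The analysis is descriptive, and no error rate or threshold is affected. This stands, but a consistent rule can still lack a reason, and none is given.
- **Equal labels are not equal thresholds.** Institutional criteria differ by tumour type, so PR need not mean the same thing everywhere. The SAP ranking is internal to INRC, and MxR is defined only in a cited source that the documents do not reproduce. This stands too. It limits the point to what the documents show, namely that INRC alone counts a category ranked below its own PR.
- **An MxR responder would usually be visible.** With few responders the listing and the category table would reveal it, and a reader could subtract. That is largely true, but the headline figure and its interval would not change.

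Two stronger readings are tempting and should not be drawn. A reader might infer that the ORR is inflated. The documents do not support that: the rule acts only if at least one INRC-assessed patient has MxR as best response, and that number may be zero. A reader might also infer that an MxR patient is a responder for ORR but not for duration of response, because Protocol 7.3.2 says "DoR is defined only for those patients with a response (CR or PR"). SAP sections 4 and 5.2.2 replace that definition with one that includes VGPR and MxR, so the two responder sets agree in the current plan.

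**Conclusion.** The unequal threshold is real and acts in one direction only. The pooled ORR can be raised, never lowered, by 1/38 = 2.6 points for each INRC patient with best response MxR, and is unchanged if there is none. This takes 38 as the denominator; the plan divides by all treated expansion patients, so the exact step is one over that number.

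No probability can be put on the effect, because the documents give neither the number of INRC patients nor the frequency of MxR. The finding is therefore that the primary rate is open to being raised by an unexplained exception, not that it has been raised. It is worth correcting because the remedy is cheap and the rate is the main evidence for the development decision.

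**What to change.** - In Protocol 7.3.1 and SAP 7.4.2, define objective response under INRC for the primary ORR as CR, VGPR or PR.
- Report the ORR and exact 95% interval including MxR as a labelled sensitivity line.
- In SAP 5.2.2, use the same responder set for duration of response, so that the two endpoints continue to agree.

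If the sponsor prefers to keep the present rule, the minimum is to print the ORR and interval without MxR beside the planned one. A stated reason for counting MxR would also help.

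The cost is a wording change in each document and one extra table line. The primary ORR may turn out slightly less favourable.

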2.2 TRIAL OBJECTIVES

The objective of the **dose finding part** is to determine the maximum tolerated dose (MTD), safety and pharmacokinetics of afatinib. The MTD of afatinib as single agent will be determined in the paediatric patient population across all applicable tumour entities, based on the occurrence of dose limiting toxicities (DLTs).

The **MTD expansion cohorts/Phase II part** will provide insight into the clinical anti-tumour activity of afatinib, i.e. efficacy of afatinib evaluated by objective response (OR), duration of objective response (DoR), progression free survival (PFS) and more data on safety and pharmacokinetics in a larger number of patients suffering from HGG, DIPG, EM and other solid tumours with ErbB pathway deregulation regardless of tumour histology will be generated.

In case the observed degree of efficacy in any of the above mentioned tumour indications within this phase I/II trial renders further development of afatinib in paediatrics suitable, additional trial(s) with single agent or combination therapy may proceed.

Proprietary confidential information.

© 2017 Boehringer Ingelheim International GmbH or one or more of its affiliated companies. All rights reserved.

This document may not - in full or in part - be passed on, reproduced, published or otherwise used without prior written permission.

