The proposed paediatric phase I/II trial is following suggestions made by PDCO during the review of afatinib's initial paediatric development plan and the FDA's written request issued April 2017 ([ra00865826](#)). The MTD expansion cohorts /Phase II part will accrue patients with HGG, DIPG, EM and any other solid tumour with ErbB deregulation as defined in sections [3.3.2](#) and [5.6](#). In addition patients with proven genomic, transcriptomic or proteomic ErbB alterations in their tumours will be recruited to an exploratory cohort. Such biomarker driven, histology agnostic development is innovative for paediatric oncology and only little precedence exists in adults (SHIVA ([R14-4174](#)), MOSCATO ([R14-4191](#); [R14-4189](#))). More recently, however, genomic screening programs were implemented in paediatric oncology (INFORM ([R14-4190](#); [R14-4233](#); [R14-4104](#))), allowing patients' early assignment to targeted treatment regimen. To enable assessment of afatinib's anti-tumour activity in this biomarker driven, largely histology agnostic approach, nevertheless a defined/ small number of patients per indication needs to be included ([ra00865826](#)). Assessment of antitumour activity for afatinib at the end of this phase I/II trial will determine future trial activities in close alignment with regulatory agencies and specialists in the field.

The trial medication is available as oral formulations, i.e. film coated tablets of various strengths for older children and an oral liquid formulation at 4 mg/ml dose strength for younger children. These oral formulations will grant patients and their parents the advantage of out-patient treatment and increase flexibility to move on with their lives. A resulting increase in quality of life, with hopefully increased efficacy should impact positively on treatment compliance.

Proprietary confidential information.

© 2017 Boehringer Ingelheim International GmbH or one or more of its affiliated companies. All rights reserved.

This document may not - in full or in part - be passed on, reproduced, published or otherwise used without prior written permission.

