
Dose finding Part: A rolling 6 design will be used to determine the MTD. The MTD will be assessed by DLT as described in [Table 4.1.4.1:2](#). The MTD will be determined as the highest dose at which no more than 1/6 patients experienced DLT. The rolling 6 design was chosen to limit the waiting period for paediatric patients seeking treatment, as depicted below.

MTD expansion cohorts/Phase II part will recruit a minimum of 5 patients in each of the four disease specific cohorts for HGG, DIPG, EM and other solid tumours fulfilling ErbB biomarker selection criteria (see [Section 3.3.2](#)) and an exploratory cohort of patients with proven genomic, transcriptomic or proteomic ErbB alterations. Efficacy will be assessed by objective response (OR) and the OR rate must be considered meaningful by experts in the field of paediatric oncology and regulatory agencies to pursue further clinical development.

Proprietary confidential information.

© 2017 Boehringer Ingelheim International GmbH or one or more of its affiliated companies. All rights reserved.

This document may not - in full or in part - be passed on, reproduced, published or otherwise used without prior written permission.

Tumour material from all patients entered into this clinical trial must be available for retrospective testing of an ErbB pathway deregulation (for DIPG in dose finding part, see [section 3.3.2](#)) or prospective patient screening into the MTD expansion cohorts/Phase II part.

Intra-patient dose escalation: No clear exposure-efficacy correlation for afatinib has been identified in adult cancer patients yet. Conventional dosing in oncology trials is based on the MTD, or a recommended Phase II dose close to the MTD, dependent on overall safety. Treatment at lower dose tiers may be hampered by a presumed lack of efficacy. Assessment of the MTD or the recommended Phase II dose in oncology trials is based on a frequency of patients with DLTs. Trial 1200.120 will allow intra-patient dose escalation. As soon as the next higher dose tier is considered safe by standard DLT incidences in course one, patients of the lower dose tier, who benefit from treatment may resume treatment at the next higher dose. Although these patients will not be counted into MTD dose cohorts – see rolling 6 design- the safety database at the MTD level/ higher dose tiers and hopefully patients' benefit from participation in Phase I dose finding will be increased.

This part has been completed ([c09990672-01](#)).

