6.3 PATIENT SETS ANALYSED

Treated set (TS):

This patient set includes all patients enrolled in the trial who were documented to have taken at least one dose of study medication.

Dose finding cohort treated set:

This patient set includes all patients enrolled in dose finding cohort of the trial who were documented to have taken at least one dose of study medication.

MTD Expansion cohort treated set:

This patient set includes all patients enrolled in expansion cohort who must satisfy the following criterion:

- Patients' tumour must be tested for positivity on 2 of the following tests: EGFR IHC>150 and/or HER2 IHC>0 and/or EGFR FISH positive and/or HER2 DDISH positive.

or

- Patient will have proven genomic, transcriptomic or proteomic alterations which are not defined above.

and

- Patients who were documented to have taken at least one dose of study medication.

PK analysis set (PKS):

This set includes all patients in the treated set (TS) who provided at least one PK endpoint that was not excluded due to a protocol deviation relevant to the evaluation of PK or due to PK non-evaluability. Thus, a patient will be included in the PKS, even if he/she contributes only one PK parameter value for one period to the statistical assessment. Descriptive and model based analyses of PK parameters will be based on the PKS.

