7.5 SECONDARY ENDPOINT(S)

7.5.1 Key secondary endpoint(s)

This section is not applicable as no key secondary endpoint has been specified in the protocol.

7.5.2 (Other) Secondary endpoint(s)

For progression free survival (PFS), objective response (OR) and duration of objective response (DoR), a descriptive and graphical summary of the endpoint will be provided. The Kaplan-Meier estimates of PFS and DoR (if applicable) and 95% confidence intervals will be calculated at the time of each planned assessment. For the dose finding part, the number of patients with OR will be summarized by dose level. If fewer than 5 patients achieved OR, then DoR will only be listed; Kaplan-Meier estimates will not be calculated and no summary table or graph will be provided.

To evaluate the potential influence of age on pharmacokinetic parameters like C_{max} and AUC, an exploratory subgroup analysis will be performed for different age groups. For this, binning of age into groups will be performed to ensure that groups have reasonable patient numbers. If feasible, a correlation of age and PK parameters may be performed.

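### The visible primary analysis text gives the expansion-part response rate only on all treated patients; add descriptive rows by cohort, because the protocol also asks about activity per indication

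*Protocol*

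**What the plan says.** **Primary figure.** Protocol 7.3.1 gives the proportion with objective response (ORR) and "the exact 95% confidence interval based on all treated patients in the MTD expansion cohorts/Phase II part". SAP 7.4.2 has the rate "reported as proportion of responders with 95% Clopper-Pearson CIs based on all treated patients".

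**Who is in it.** SAP 6.3 defines one expansion treated set. It takes patients positive on two of the four named markers, and also the exploratory route: "Patient will have proven genomic, transcriptomic or proteomic alterations which are not defined above". Protocol 4.1.2 requires central confirmation for cohorts 1-4 and a laboratory report for cohort 5. Protocol 3.1 caps the exploratory cohort at 6.

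**Splits and listings.** The only split of response named in the visible text is in SAP 7.5.2: "For the dose finding part, the number of patients with OR will be summarized by dose level". SAP 7.4.2 adds: "If only few patients (fewer than 5) achieved objective response, a detailed listing will be reported". The columns of that listing are not stated.

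**What the response data are for.** Two aims appear side by side.
- Per indication: Protocol 2.2 links possible further trials to "the observed degree of efficacy in any of the above mentioned tumour indications". Protocol 2.3 says that "a defined/ small number of patients per indication needs to be included". Protocol 3.2 criticises earlier broad trials because they could not give an effect size for each indication. Protocol 7.6 sets a minimum of 5 in each of four cohorts, and Table 7.6:1 works per cohort.
- Overall: Protocol 3.3 describes proof of concept in ErbB-deregulated patients, and Protocol 5.6.1 refers to the response level of the expansion part as a whole. Protocol 3.2 says that "the OR rate must be considered meaningful by experts in the field of paediatric oncology and regulatory agencies to pursue further clinical development".

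**The concern.** The design secures a minimum number of patients in each indication, but the visible primary analysis does not report by indication. Protocol 7.2 plans no hypothesis test and no numerical threshold is set, so experts and regulators will work from the reported rates themselves. A single rate cannot show whether responses come from high grade glioma, diffuse intrinsic pontine glioma, ependymoma, the mixed cohort or the exploratory cohort. Nor can it separate patients confirmed centrally on the selection markers from those who entered on a laboratory report. What is at stake is how a descriptive result is read; no error rate is affected.

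**Working it through.** **Inputs.** Up to 38 patients evaluable for response (protocol synopsis; Protocol 3.3). Minimum of 5 in each of cohorts 1-4 (Protocol 7.6). Maximum of 6 in cohort 5 (Protocol 3.1). Illustrative response rates of 20% and 30% (Table 7.6:1).

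**1. The plan's own table.** With n patients and true rate p, P(0) = (1-p)^n and P(2 or more) = 1 - (1-p)^n - np(1-p)^(n-1). For n = 5:
- p = 20%: 32.8% for none, 67.2% for one or more, 26.3% for two or more (table: 32.8, 67.2, 26.2).
- p = 30%: 16.8%, 83.2%, 47.2% (table: 16.8, 83.2, 47.1).

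All cells of Table 7.6:1 agree within 0.1 point except one. For n = 6, p = 30%, two or more responses: 1 - 0.7^6 - 6 x 0.3 x 0.7^5 = 58.0%, where the table has 60%. That cell does not bear on this point.

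**2. Cohort sizes (assumed).** Take 38 treated, with cohort 5 full. Places above the minimums: 38 - 4 x 5 - 6 = 12. Shared equally, each of cohorts 1-4 has 5 + 3 = 8. If one cohort takes all 12, it has 17 and the other three have 5.

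**3. Same overall result, different patterns.** Five responders is the smallest number at which the listing is no longer required. Intervals are Clopper-Pearson 95%. The all-treated result is 5/38 = 13.2% (4.4-28.1) in every row.

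| Where the 5 responders are | Result by cohort or route |
|---|---|
| All in one cohort of 8 | 5/8 = 62.5% (24.5-91.5); 0/8 (0-36.9) in each of the other three |
| One in each of the five cohorts | 1/8 = 12.5% (0.3-52.7) in each of cohorts 1-4; 1/6 = 16.7% (0.4-64.1) in cohort 5 |
| All in one cohort of 17 | 5/17 = 29.4% (10.3-56.0) there |
| All in cohorts 1-4 | 5/32 = 15.6% (5.3-32.8) for cohorts 1-4 combined |
| Two in cohort 5 | 3/32 = 9.4% (2.0-25.0) for cohorts 1-4 combined |

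**4. How often the listing is required.** This is P(X <= 4) for a binomial number of responders X.

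| Assumed truth | Listing required |
|---|---|
| One cohort at 30%, no response elsewhere, n = 5 | 99.8% |
| Same, n = 8 | 94.2% |
| Same, n = 10 | 85.0% |
| Same, n = 17 | 38.9% |
| 10% in all 38 | 67.0% |
| 20% in all 38 | 9.9% |
| 30% in all 38 | 0.4% |

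The listing is therefore nearly always produced when a single small cohort responds. It is less often produced when the responding cohort is large, and rarely when 20% or 30% holds in all 38.

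**The case against.** **The absence cannot be proved.** The SAP as available skips sections 5.3, 5.4, 6.4, 7.6 and 9, and SAP 7.7 cites a Section 5.4 that is not shown. The disease control endpoint in the SAP's history table also appears nowhere else. A breakdown by cohort could sit in that text. This stands: a reader might infer that the SAP has no response rate by cohort anywhere, and the documents do not support that.

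**The decision is partly on the whole expansion part.** Protocol 3.2, 3.3 and 5.6.1 speak of the response rate or activity across the selected patients, and the per-indication remark in Protocol 2.3 comes within a largely histology-agnostic approach. This also stands. A reader might infer that pooling is wrong, or that the protocol judges activity only by indication; neither follows.

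**The quoted words fix a denominator, not a layout.** They do not forbid a table by cohort. That is true, but they do not provide for one either, and the authors named a split where they wanted one, by dose level in the dose finding part.

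**The listing protects where pooling misleads most.** This largely holds for small cohorts: in the 8-patient example, five or more responders would occur only 100 - 94.2 = 5.8% of the time at 30%. Where the listing usually drops out, at 20% or 30% in all 38, the pooled rate is representative if response really is uniform. But a reader of the pooled rate alone cannot tell that it is uniform, and the listing gives no denominator, rate or interval by cohort.

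**Conclusion.** The point holds for the visible primary analysis sections, Protocol 7.3.1 and SAP 7.4.2. The all-treated rate is a valid primary figure for the overall proof-of-concept judgement and should stay. It cannot answer the per-indication question that Protocol 2.2, 2.3, 3.2 and Table 7.6:1 also set up, and it combines two selection routes. In the worked example, a reported 13.2% is compatible with 62.5% in one cohort and none elsewhere, or with one responder in each cohort. The example assumes that 38 patients are treated, that cohort 5 is full and that cohorts 1-4 are equal in size. The listing frequencies assume binomial response at the stated rates. Since nothing is tested and the listing covers much of the sparse-response case, this is worth considering and at most a low-priority recommendation.

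**What to change.** Unless SAP text that is not visible already does so, amend SAP 7.4.2 and record the change in SAP section 4:
- Keep the all-treated ORR with its exact interval as the primary figure.
- Add descriptive rows with n, ORR and Clopper-Pearson 95% CI for each cohort, with cohort 5 separate, and for cohorts 1-4 combined.
- Show cohort in the responder listing.

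The cost is SAP wording and extra rows in one table. No new data are needed, and no protocol amendment, because the primary figure is unchanged. The drawback is very wide intervals: 0/5 gives 0-52.2%, 1/5 gives 0.5-71.6%. The rows should be labelled descriptive and not read as tests. Naming them in advance also avoids choosing after the fact which cohorts to show.

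A separate small correction: in Table 7.6:1, the probability of two or more responses for n = 6 and a 30% rate should read 58.0%.
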